6.2.3 Treatment and Assessments

Patients will not be randomized; patients will be treated as described before. For this pilot study, a course of therapy is 28 day. We are allowing a treatment window of \pm 1-3 days. Lapatinib will be administered before Veliparib. Patients will be restaged with the same images or staging studies used in the baseline evaluation (staging studies are defined as studies contributing to response evaluation, e.g. CTs (chest, abdomen, pelvis), MRI, bone scan, PET, or plain x-rays every 8 weeks (as an example, before course 3, 5, 7, 9, ..), and tumor response defined by RECIST criteria version 1.1. Patients with SD, PR or CR may continue therapy until disease progression or intolerance to therapy. An EKG will be obtained on day 2 and 3 of cycle one. Also, an EKG will be obtained on day one of each subsequent cycle. Echocardiogram will be obtained every 3 months.

In addition, patients will undergo performance status, CBC with differential and platelets, CMP, concomitant medication assessment; and assessment of adverse events on day 1 of each cycle. Hypocalcemia, hypokalemia, and hypomagnesemia will be corrected prior to lapatinib administration. Physical evaluation, vital signs, and weight will be performed day 1 of each cycle. CA27.29 will be obtained every 8 weeks. Pharmacokinetic samples are described in section 6.3.

Patients who have a $\geq 20\%$ decrease in left ventricular cardiac ejection fraction relative to baseline, and the ejection fraction is below the institution's lower limit of normal, should have a repeat evaluation of ejection fraction 1-2 weeks later while still receiving investigational product. If the repeat ejection fraction evaluation confirms a $\geq 20\%$ decrease in left ventricular cardiac ejection fraction, and the ejection fraction is below the institution's lower limit of normal, then lapatinib should be temporarily discontinued. If the left ventricular ejection fraction recovers during the next 3 weeks, the patient may be restarted on investigational product at a reduced dose. For such patients, monitoring of left ventricular ejection fraction will then be performed 2 weeks and 4 weeks after rechallenge, and then every 4 weeks thereafter. If repeat ejection fraction evaluation still shows a decrease $\geq 20\%$ in left ventricular ejection fraction relative to baseline, and the value is below the institution's lower limit of normal, then the subject should be withdrawn from investigational product. Patients with an NCI CTCAE grade 3 or 4 LVEF relative decrease must be withdrawn from study medications. Patients will be monitored closely for pulmonary toxicity. Patients with an NCI CTCAE Grade 3 or 4 interstitial pneumonitis must be withdrawn from study medications.

6.2.4 Post-treatment/Follow-up Assessments

Patients will be taken off study treatment following progression; patients will also be taken off treatment for treatment delay of more than 2 weeks, or concurrent illness that in the opinion of the investigator would affect clinical assessment or endanger the patient. In the event of refusal of further therapy, the patient will continue to be followed for outcome. Only if the patient withdraws consent will outcome data cease to be collected.

The following evaluations and procedures will be performed at **early termination** (discontinuation for any reason before documentation of disease progression): clinical evaluations (weight, physical examination, vital signs and performance status); there must be a complete and clear documentation

of objective response or disease progression (staging studies are defined as studies contributing to response evaluation, e.g. CTs (chest, abdomen, pelvis), MRI, bone scan, PET, or plain x-rays using the RECIST criteria version 1.1 (reason(s) for discontinuation must be documented); laboratory assessment (CBC with differential and platelet count, and CMP); concomitant medication assessment; and assessment of adverse events (if the patient has an ongoing toxicity, the patient should be followed until resolution or stabilization. Serious and non-serious adverse events occurring within 30 days of day 0 of the last treatment should be reported on the appropriate adverse event CRF).

6.3 Ancillary Studies

Pharmacokinetics for Lapatinib and Veliparib In this pilot trial, pharmacokinetics will be done in all patients enrolled in the trial. Pharmacokinetics will be carried out during the first course of therapy. Samples for the first day will be collected 5 minutes before start of the therapy, 30 and 60 minutes after the first dose of Lapatinib and then 2, 4, 6, 8, and 24 hours after the start of the therapy with Lapatinib, On day 2, patients will take the dose of Lapatinib and Veliparib at the same time of day 1 and samples will be taken 30 and 60 minutes after the first dose of Lapatinib and Veliparib, then 2, 4, 6, 8, and 24 hours. Additional samples will be taken on day 3, before the third day dose of Lapatinib and Veliparib. Same schema will be followed on days 8, 9 and 10 as on days 1, 2, and 3. A total of 3-5 mL of blood will be collected in red top tubes at each of the described time points. The actual time of administration of each agent and sample collection should be recorded. See section 7.6 of the protocol for statistical analysis of pharmacokinetics. PK analysis will be conducted at UAB: PK/PD Shared Facility of the UAB Comprehensive Cancer Center.

MicroRNA Profiling Serum (serum separator tubes) will be sent to [name] lab at Georgetown University to establish microRNA profiles in serum that can predict treatment response or resistance. A genome wide analysis of the microRNA's that are detectable in serum to derive a subset of informative microRNA's will be run. A genomic wide analysis will be run on a subset of 5 patients before and after treatment to find the most informative microRNA's (Before initiation of therapy and then on day 8, 15 and 29). Informative microRNA's are defined by: the effect of treatment (longitudinal=before/after treatment); and disease status or inter-individual differences among the patients (horizontal comparison). From the serum samples sent for this analysis, only a small amount of serum is needed for this analysis. Serum that is left over after this analysis is completed will be sent back to UAB to facilitate the other correlative work for this protocol. No funding is necessary to conduct the evaluation in the laboratory; funds are needed only for shipping.

Biopsies –

A tumor biopsy of one of the metastatic lesions (see eligibility criteria for biopsy guidelines) will be obtained before initiation of therapy. Biopsy samples will preferably be obtained using a 14-18 gauge core needle; **at least** two core biopsies will be obtained and snap frozen individually for gene expression; a **third** core will be used for the preparation of paraffin-embedded blocks or formalin fixed tissue.

Biopsy of a metastatic lesion is not required for protocol entry but all patients with reasonably accessible lesions (chest wall, breast, skin, subcutaneous, superficial lymph nodes, bones and liver metastases) must agree to biopsy. Lung biopsies are not acceptable for research only. Biopsies may be done with local anesthesia or intravenous conscious sedation, according to standard institutional guidelines. If a biopsy requires general anesthesia, then it is only allowed **if** acquisition of tissue is necessary for clinical reasons (i.e. is clinically indicated), and excess tissue that would otherwise

have been discarded is then used for research purposes. If a biopsy requires general anesthesia, then a biopsy of that site for research purposes only, *without* a coexisting clinical indication is not allowed on this protocol. Patients with reasonably accessible lesions as described above, who will not agree to the biopsy, will not be enrolled in the trial. Patients with NO reasonably accessible lesions as described above can be enrolled in the trial.

Two of the snap frozen research biopsies will be sent to [name] laboratory located at the Hazelrig Salter Radiation Oncology Center ([name], [contact], lab pager [name]) where biopsies will be stored for batching. All samples will be indelibly labeled with the appropriate study number, and date of acquisition; these data will be correlated with clinical efficacy including complete response and objective response. One of the frozen research biopsies will be processed for targeted gene expression analysis, tumor microRNA profiling, and copy number variation of commonly amplified or deleted genes in cancer using the Nanostring nCounter DX system with FLEX configuration ([name] Lab). This system will also allow for the analysis of the Prosigna Breast Cancer Prognostic Gene Signature Assay (based on the PAM50 gene set established by Charles Perou et al., *Nature* 2000) that provides intrinsic subtyping information as well as prognostic information as it relates to drug response. Targeted gene expression will be performed using prebuilt gene panels by Nanostring including the Human Kinase (519 kinases), Human Immunology (594 immunology genes), Human Cancer Reference (236 cancer related genes), and Human Inflammation (184 inflammation gene) kits. Tumor microRNA profiles will also be analyzed using total RNA from tumor biopsies (800 human miRNAs). Lastly, copy number variation of commonly altered genes in cancer will be investigated from DNA harvested from the tumor. For each analysis, as little as 100ng of total RNA or 300ng of genomic DNA is needed for highly reproducible results. Additionally, if available, formalin-fixed paraffin-embedded tissues from the original primary tumor will also be subjected to this analysis to investigate the evolution of the tumor from primary to metastatic.

Fifteen slides will also be prepared from the formalin-fixed paraffin embedded tissue for analysis by conventional IHC of ER, PR, Her-2, EGFR, PARP, Ki67, apoptotic markers, and biomarkers of DNA repair such as H2AX, PARP, and BRCA localization. All samples will be indelibly labeled with the appropriate study number, and date of acquisition; these data will be correlated with clinical efficacy including complete response and objective response.

The second frozen core research biopsy will be sent to Hudson Alpha Institute at a later designated time point to be used for comprehensive genomic analysis such as Next-GEN genomic analysis.⁷¹ "Next-GEN genomic analysis will be done at HudsonAlpha Institute for Biotechnology in Huntsville, Alabama (Shared Facility of the UAB Comprehensive Cancer Center) by [name] group. No funding is necessary to conduct the evaluation in the laboratory at this time or macro-dissection; funds are needed only for shipping.

Researchers at HudsonAlpha Institute for Biotechnology led by [name] will obtain tissues from [name] and colleagues at UAB from patients with TNBC enrolled in the pilot Study. HudsonAlpha Institute for Biotechnology will analyze the tissues for several functional genomics features on a genome-wide scale, as well as whole exome DNA sequencing, to identify genetic variants. The functional genomics readout and genetic variation measurements will be assessed to help identify differences associated with TNBC itself, subtypes of TNBC and/or responses to drug treatments. The researchers at Hudson will utilize their expertise in applying six different genome-wide functional genomics measurements, as well as whole exome sequencing, whole genome sequencing and specialized array-based genotyping to measure genomic and genetic variants for cancers, brain diseases, autoimmune diseases and drug responses.

The functional genomics measurements will include the use of ultrahigh throughput sequencing to measure mRNAs and long non-coding RNAs (RNA-seq), microRNAs (miRNA-seq), DNA methylation (a combination of two approaches, RRBS and Methyl1450 arrays), protein:DNA interactions (ChIP-seq), chromatin markers (also ChIP-seq) and chromatin accessibility measurements (DNase-seq).

To measure DNA sequence variation, two types of ultrahigh throughput DNA sequencing will be performed: whole exome sequencing, where all the exons and exon:intron boundaries in the human genome are sequenced deeply; and whole genome sequencing, to be used on a modest number of samples due to expense. A combination of exome and whole genome sequencing with inexpensive genotyping of 1 million or more polymorphic DNA markers around the genome may be used to supplement the DNA sequencing and to improve the ability to identify large DNA sequence variants known as copy number variants.

Fifteen slides will be prepared from the paraffin blocks or formalin fixed tissue by a designated pathologist at UAB for analysis by conventional IHC of ER, PR, Her-2, EGFR, Ki67, apoptotic markers, and biomarkers of DNA repair such as H2AX and BRCA localization. All samples will be indelibly labeled with the appropriate study number, and date of acquisition; these data will be correlated with clinical efficacy including complete response and objective response.

Any leftover study blood and tissue samples may be stored for future research studies. The subjects will consent to the future use of samples in the consent form for the study. Any samples will only be released for use in future studies after approval by the Principal Investigator and other regulatory bodies, as appropriate.

Pharmacogenomic Analyses – Blood samples for pharmacogenomic analyses will be collected on a first day before initiation of research agents. Blood will be collected into one 6 ml K₂EDTA polypropylene blood collection tube (Becton-Dickinson) and into one PAX gene tube. The 6 mL polypropylene K₂EDTA tube will be placed in an ice bath immediately following collection and stored upright in a freezer set at -20°C (+/- 10°C) until sending to the laboratory. It is important to collect a full tube of whole blood. The PAX gene tube should be stored upright at room temperature for a minimum of 2 hours or a maximum of 4 hours before processing or transferring to a freezer. They should be stored upright in a wire rack and stored at -20 degrees Celsius or colder until sending to the laboratory. Blood samples should be sent to The University of Alabama (Attention: The University of Alabama at Birmingham; Center for Clinical Translation Science (CCTS) Laboratory, [name]) as soon as logistically possible following blood draws. The University of Alabama will store the samples until assays are to be performed. Samples will be shipped to The HudsonAlpha Institute for Biotechnology. The Hudson Alpha Institute may conduct pharmacogenomic assays possibly including, but not limited to, DNA sequencing of exons as well as DNA sequencing from RNA transcripts, DNA methylation screens, and tests for specific single nucleotide polymorphisms. These tests on normal tissue may provide reference values for comparison against similar tests previously approved for the patients' tumor tissue. The protocol will provide the tubes (EDTA and PAX gene tubes).

Plasma Tumor DNA (ptDNA)-

Successful treatment depends on the ability to monitor disease burden and response to therapies. Recently, a proof of principle study has shown that plasma tumor DNA (ptDNA) can be used as a reliable breast cancer biomarker in metastatic disease, due to its sensitivity and wide dynamic range. ptDNA more accurately reflects changes in response to therapies, and absolute levels of ptDNA

demonstrate prognostic significance. Thus, ptDNA as a liquid biopsy shows great promise in the clinical management of metastatic breast cancer. The key is to maximize removal of contaminating cells and genomic DNA from these cells as large genomic DNA fragments hinder plasma DNA analysis.

It is now well-established that cells naturally secrete or shed small DNA fragments into the circulation with most of this DNA being compartmentalized in the plasma component of whole blood. Small amounts of cell-free circulating DNA can be detected in plasma from healthy individuals,^{79,80} is often highly elevated in metastatic cancer patients^{79,81} and correlates with disease burden.^{78,82,83} Interestingly, how ctDNA enters the plasma is not precisely known. While the fragment size of circulating DNA in healthy individuals suggests that it originates from apoptotic cells,⁸⁰ circulating DNA is also shed from non-apoptotic cells and in this instance it is often larger and more variable in size.^{84,85,86} For clarity, we prefer and will henceforth use the term plasma tumor DNA (ptDNA) over ctDNA since there is confusion regarding ctDNA versus DNA derived from CTCs, which are distinctly different. In addition, ptDNA is more specific as it is a subset of ctDNA, since ctDNA also includes urine tumor DNA (utDNA) as well as ctDNA in other bodily fluids. Recent work, including that from our own group, supports the utility of ptDNA as a facile means for liquid biopsy.^{78,81,87} [name]'s group and others have shown that cancer specific somatic mutations can be detected in ptDNA from metastatic breast cancer patients with up to a 100% concordance when blood is taken concurrently with tissue biopsy.^{78,81,87} In contrast, [name] group also demonstrated that mutational discordance can occur between ptDNA and primary breast cancer tissues when there is a prolonged period (greater than 3 years) between initial diagnosis and recurrence.⁸⁷ This speaks to the now proven concept of tumor heterogeneity and clonal evolution. ptPtDNA has also been used to identify treatment associated mutational changes.^{77,81} Thus, assessment of ptDNA can relay the mutational status of a patient's cancer with the ability for serial testing.

Blood will be collected in three cell-free DNA BCT tubes (Streck) per time point: at baseline before drug administration, on days 15 and 29 (day 1 of cycle 2 pre-treatment). Samples collected in the DNA BCT tubes are stable for up to 14 days at temperatures between 6-37° C. Once tubes are filled completely the tube should be mixed by gently inverting 8 to 10 times. The tubes will be transferred to [name] lab for processing and freezing of the samples which will be batched and sent at a later date for analysis to [name]'s lab at the Sidney Kimmel Comprehensive Cancer Center, Johns Hopkins University.

Serum Marker of Apoptosis - Serum levels of M30 will be drawn pre-dose, Day 8, and Day 15 of cycle one only. The changes of the serum levels of M30 at each time point will be correlated with levels of M30 in CTCs as well as with efficacy parameters. M30 serum evaluations will be conducted at the Mayo Clinic by [name]. Activation of the intrinsic apoptotic pathway involves release of cytochrome c to the cytosol, activation of caspases (specifically caspase 9 followed by caspase 3), and cleavage of hundreds of substrates by caspase 3.^{72,73} Among the caspase 3 substrates is cytokeratin 18, which yields a fragment that is uniquely detectable using the monoclonal antibody M30 upon caspase cleavage.⁷⁴ When apoptotic cells lyse, all of these proteins (cytochrome c, cleaved/activated caspase 3 and cleaved cytokeratin 18) are released to the circulation, where they can be detected by ELISA to provide an assessment of the degree of epithelial cell apoptosis. Samples will be sent to Mayo Clinic for later analysis. No funding is necessary to conduct the evaluation in the laboratory; funds are needed only for shipping.

6.4 Subject Discontinuation/Early Termination

Patients may withdraw from this study at any time. Any patient who withdraws will be encouraged to return to the study center for the post-dose evaluations. The termination visit consists of all evaluations scheduled for the termination visit. The primary reason(s) for discontinuation must be recorded on the appropriate CRF page. The PI may discontinue a patient from treatment. Reasons may include, but are not limited to, the following: clinically significant deterioration, noncompliance, persistent grade 3 or 4 adverse event or any significant adverse event that compromises the patient's ability to participate in the study, requirement of a significant surgical procedure or radiation therapy during the treatment period of the study, investigator's determination that it is not in the patient's best interest to continue participation, development of brain metastases, or pregnancy. Patients will be monitored for 30 days following the end of treatment and will be removed from the study at the end of this follow-up period. Patients who have an ongoing research-related Grade 4 or serious adverse event at the time of discontinuation from study treatment will continue to be followed until resolution of the event or until the event is considered irreversible.

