4.3 Withdrawal of Patients

A patient should be withdrawn from the trial treatment if, in the opinion of the investigator, it is medically necessary, or if it is the wish of the patient. If a patient does not return for a scheduled visit, every effort should be made to contact the patient. In any circumstance, every effort should be made to document patient outcome. Patients should be removed from therapy if any of the following occurs:

- Disease progression in patients receiving the combination of Lapatinib and Veliparib. Every effort should be made to document objective evidence of tumor progression radiographically and not solely based on clinical and/or tumor marker suggestions of progression.
- The occurrence of unacceptable toxicity indicating the need for cessation of treatment. Patients will be followed until stabilization or resolution of the toxicity.
- The physician feels it is in the best interest of the patient to stop treatment.
- Patient refusal to continue with therapy.
- Non-compliance by the patient with protocol requirements.
- Patient is lost to follow-up. If a patient does not return for scheduled visits, every effort should be made to re-establish contact. In any circumstance, every effort should be made to document patient outcome, if possible.
- Patient becomes pregnant.
- Termination of the study by investigator industry partners.

Treatment may be delayed for up to 2 weeks beyond planned resumption of the next cycle. If a patient does not fulfill re-treatment criteria by that time, they will be removed from the trial; if unacceptable toxicity to one of the agents used in this combination occurs in a patient enrolled in the study, then patient will NOT continue on a single agent.

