6.7.4 Evaluation of Best Overall Response

The best overall response is the best response recorded from the start of the treatment until disease progression/recurrence (taking as reference for progressive disease the smallest measurements recorded since the treatment started). The patient's best response assignment will depend on the achievement of both measurement and confirmation criteria.

For Patients with Measurable Disease (i.e., Target Disease)				
Target Lesions	Non Target Lesions	New Lesions	Overall Response	Best Overall Response when Confirmation is Required*
CR	CR	No	CR	\geq 4 wks. confirmation**
CR	Non-CR/Non-PD	No	PR	\geq 4 wks. confirmation**
CR	Not evaluated	No	PR	
PR	Non-CR/Non-PD/not evaluated	No	PR	
SD	Non-CR/Non-PD/not evaluated	No	SD	Documented at least once \geq 4 wks. from baseline**
PD	Any	Yes or No	PD	No prior SD, PR or CR
Any	PD***	Yes or No	PD	
Any	Any	Yes	PD	

* See RECIST 1.1 manuscript for further details on what is evidence of a new lesion.
 ** Only for non-randomized trials with response as primary endpoint.
 *** In exceptional circumstances, unequivocal progression in non-target lesions may be accepted as disease progression.

Note: Patients with a global deterioration of health status requiring discontinuation of treatment without objective evidence of disease progression at that time should be reported as "symptomatic deterioration". Every effort should be made to document the objective progression even after discontinuation of treatment.

For Patients with Non-Measurable Disease

(i.e., Non-Target Disease)

Non-Target Lesions	New Lesions	Overall Response
CR	No	CR
Non-CR/non-PD	No	Non-CR/non-PD*
Not all evaluated	No	Not evaluated
Uequivocal PD	Yes or No	PD
Any	Yes	PD

* "Non-CR/non-PD" is preferred over "stable disease" for non-target disease since SD is increasingly used as an endpoint for assessment of efficacy in some trials so to assign this category when non-lesions can be measured is not advised.

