7.5 Analysis plan

We will consider that any subjects enrolled to the study as intent-to-treat (ITT) population; patients must at least start therapy or they will be replaced. The ITT patients will be included for all efficacy analysis. We will consider any patients who received at least one dose of Lapatinib and/or Veliparib as safety analysis population. The safety analysis population will be used for safety evaluation. The final statistical analysis will be conducted after all patients that have completed treatment with documentation of toxicity, response and progression free survival.

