7.7 Study Accrual

We plan to enroll a total of 20 subjects from a single institution (University of Alabama at Birmingham). We expect that the enrollment will be completed in 12-18 months. The study will be stopped 3 months after the last patient completes the therapy.

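### Section 6.4 takes patients off study 30 days after treatment ends, which contradicts 6.2.4, and no PFS censoring rule settles which applies

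*Combined protocol and SAP*

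**What the plan says.** Three parts of the combined protocol and SAP set the end of follow-up, and they differ.

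- **6.4 Subject Discontinuation/Early Termination:** "Patients will be monitored for 30 days following the end of treatment and will be removed from the study". The one stated extension is for an ongoing research-related Grade 4 or serious adverse event.
- **6.2.4 Post-treatment/Follow-up Assessments:** "In the event of refusal of further therapy, the patient will continue to be followed for outcome". The general rule comes next: "Only if the patient withdraws consent will outcome data cease to be collected".
- **7.7 Study Accrual:** "The study will be stopped 3 months after the last patient completes the therapy".

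Two other places lean towards continued follow-up, without a duration or scan schedule. Section 4.3 says "In any circumstance, every effort should be made to document patient outcome". Section 6.7.4, on patients stopped for global deterioration, says "Every effort should be made to document the objective progression even after discontinuation of treatment".

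Section 6.7.6 defines PFS from study entry to progression or death. Section 7.5.2 estimates the median by Kaplan-Meier with a 95% confidence interval and also uses PFS in exploratory log-rank and Cox biomarker analyses. Section 7.5 times the final analysis as "conducted after all patients that have completed treatment with documentation of toxicity, response and progression free survival". No censoring rule is stated. The 6.6 schedule has staging every 8 weeks, at progression and at end of treatment or early termination, with no column after that.

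**The concern.** Patients can leave treatment without progression for several reasons: unacceptable or recurrent toxicity, a delay of more than two weeks, repeated compliance below 75%, clinical deterioration, or refusal. For such a patient who has not withdrawn consent, 6.4 ends participation at 30 days while 6.2.4 keeps outcome collection open. Site staff cannot follow both.

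If 6.4 is followed, later progressions and deaths in these patients are not recorded. Fewer events mean a wider interval for the median and weaker biomarker analyses. In addition, Kaplan-Meier assumes that a censored patient has the same future risk as those still under observation. Section 6.4 itself lists deterioration and persistent grade 3 or 4 adverse events as reasons to stop, so that assumption could fail.

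**Working it through.** **1. No PFS figure to reproduce.** The plan gives no expected PFS, event count, dropout rate or censoring share. What follows is illustration on stated assumptions.

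**2. The text side by side, for a patient who stops for toxicity, has not progressed and keeps consent.**
- 6.4: off study at 30 days, unless a qualifying adverse event is ongoing.
- 6.2.4: outcome data continue.
- 4.3: outcome to be documented, with no end date.
- 7.7: the study stays open until three months after the last patient's therapy, which for an early enrollee may be much later than 30 days after stopping.

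Routine scans are 8 weeks (56 days) apart. After a termination scan, the next one on that interval would fall outside a 30-day window, so the termination scan could in practice be the last assessment.

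**3. Inputs.**
- 20 patients (7.4).
- On-drug median 2.8 months. This is the historical time to progression for triple-negative patients in section 2.1, used only as a scale. Exponential hazard λ = ln 2 / 2.8 = 0.2476 per month.
- Assumed: a share s of 20-60% is assigned a stop time, uniform over the first 2.5 months.
- Assumed: hazard after stopping is h times the on-drug hazard, with h from 0.5 to 2.
- 30 days is taken as one month.

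**4. Events lost with the hazard unchanged (h = 1).**
- Chance that an assigned stop comes before progression: (1 − e^(−2.5λ)) / (2.5λ) = (1 − 0.5385) / 0.6189 = 0.7456.
- Chance of no event in the next month: e^(−λ) = 0.7807.
- Events lost under 6.4 = 20 × s × 0.7456 × 0.7807.
- s = 20%: 2.33 lost, leaving 17.7. s = 60%: 6.99 lost, leaving 13.0.
- If the termination scan is the last assessment, the factor 0.7807 drops out, leaving 17.0 and 11.1.

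The comparator of 20 events is a ceiling. It assumes every patient is followed to an event, whereas the 7.7 close would still censor some.

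**5. Median PFS, by simulation of the same model** (months; excesses taken before rounding).

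| s | h | Full follow-up | 30-day capture | Last look at stopping | Excess, 30-day | Excess, at stopping |
|---|---|---|---|---|---|---|
| 20-60% | 1 | 2.80 | 2.80 | 2.80 | 0 | 0 |
| 20% | 1.5 | 2.67 | 2.71 | 2.80 | 0.04 | 0.13 |
| 20% | 2 | 2.57 | 2.63 | 2.80 | 0.06 | 0.22 |
| 60% | 1.5 | 2.46 | 2.53 | 2.80 | 0.07 | 0.34 |
| 60% | 2 | 2.25 | 2.34 | 2.80 | 0.08 | 0.55 |
| 30% | 0.5 | 3.11 | 2.96 | 2.80 | −0.14 | −0.31 |

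Closed-form check of the largest case (s = 0.6, h = 2). For t ≤ 2.5, S(t) = (1 − s)e^(−λt) + s[(1 − t/2.5)e^(−λt) + (e^(−λt) − e^(−2λt)) / (2.5λ)]. At t = 2.254 this is 0.4 × 0.5724 + 0.6 × [0.0984 × 0.5724 + 0.3955] = 0.500, so the median with full follow-up is 2.25. Censoring at stopping leaves only the on-drug hazard, so Kaplan-Meier returns 2.80.

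**6. Different stopping pattern.** With stopping at a constant rate instead, 30% stopping before progression and h = 2, the medians are 2.53 with full follow-up, 2.61 with 30-day capture and 2.79 if the last look is at stopping. The excesses are 0.08 and 0.26, of the same order.

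**7. Against sampling error.** With 20 exponential times and a 2.8-month median, the sample median has a standard deviation of about 0.9 month (95% range about 1.4 to 4.9).

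**The case against.** The strongest reply is that the 30 days in 6.4 is a safety window. It matches the 30-day adverse-event reporting periods in 6.2.4 and 9.1.2, and the next sentence of 6.4 concerns ongoing adverse events. Sections 4.3, 6.2.4 and 6.7.4 all point to continued outcome documentation, and staging at early termination captures progression already present at stopping. On that reading no PFS data are lost. This is a natural reading and may be what was meant, but 6.4 says removed from the study, and its exception does not cover efficacy follow-up. The contradiction in wording stands.

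A second reply is that the effect on the median is small. That also stands: with 30-day capture it is a few hundredths of a month, against sampling error of about 0.9 month.

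A reader might infer four stronger things that the documents do not support.
- **That PFS is informatively censored as planned.** No section censors PFS at 30 days. It follows only if 6.4 governs and stopping is linked to later risk.
- **That the bias favours the combination.** The trial has one arm, and the direction depends on the hazard after stopping, which the documents do not give.
- **That an on-drug median of 5.7 months makes the bias larger.** The only such figure (section 2.2) is for olaparib in BRCA mutation carriers, whom 4.1 excludes.
- **That 7.7 limits each patient to three months.** It counts from the last patient's completion of therapy.

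**Conclusion.** Wrong as written: an internal contradiction of minor to moderate severity. Sections 6.4, 6.2.4 and 7.7 give different ends to follow-up, and no censoring rule resolves them.

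Loss of events under 6.4 needs no assumption that risk changes on stopping, although the count does depend on how many stop early. The 13 to 17.7 events assume a 2.8-month median and 20-60% assigned an early stop. Bias in the median is only a possibility. At 1.5-2 times the hazard it is about 0.04-0.08 month with 30-day capture, and up to about 0.5 month only if the termination scan is in effect the last look.

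PFS is a descriptive secondary endpoint and the biomarker work is exploratory. The primary safety endpoint and the 30% response criterion for a phase II proposal (7.4) do not depend on it.

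**What to change.** - **6.4:** limit the 30-day rule to adverse-event collection, and state that stopping treatment does not end PFS follow-up.
- **6.2.4, 6.6 and 7.7:** follow every patient who has not withdrawn consent for progression and death until the 7.7 close, whatever the reason for stopping, using standard-of-care scans and chart review. Add a post-treatment column to the schedule.
- **7.5.2:** state that PFS is censored at the last adequate tumour assessment, say how new anticancer therapy is handled, and add a sensitivity analysis that counts stopping for toxicity or deterioration as an event.

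The cost is protocol wording and a few chart checks in about 20 patients at one site, with no extra mandated scans. The drawback is that off-treatment scans will fall at irregular times, so some progression dates will be less exact. Progression not recorded at the time may be hard to recover later, so the wording is best settled before patients come off treatment.
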